**Figure 1 Procedures for intervention delivery and data collection**

**Stage 1:** the PA training on this stage will consist of two 30-min aerobic sessions per week at a moderate intensity of 30-40% of maximal heart rate reserve (% HRRmax), Equations 1 and 2. Maximal heart rate (HRmax) will be predicted using Fernhall's equation for children with ID (Fernhall 2001), where HRmax (in beats/min) = 189 - 0.56 × age (in years). For example, for a 15-years-old participant with a measured resting heart rate (HRrest) of 70 beats/min, his/her target exercise heart rate (exercise HR) will be 114 beats/min to reach 40% HRRmax (Equation 3). We adopted the % HRRmax method because it is more precise than % HRmax, as it considers individual variability of HRrest. We did not adopt the percentage of maximal oxygen uptake (% VO2max) method as it may result in negative consequences to measure or predict VO2max among children with ID (Abut 2015).

$$\% HRR_{max} = \frac{\text{exercise HR} - \text{HRrest}}{\text{HRR}} \times 100\% \quad \dots \dots \dots \text{Equation 1}$$

$$\text{HRR} = \text{HRmax} - \text{HRrest} \quad \dots \dots \dots \text{Equation 2}$$

$$\text{exercise HR} = \% HRR_{max} \times (\text{HRmax} - \text{HRrest}) + \text{HRrest} \quad \dots \dots \dots \text{Equation 3}$$

where, % HRRmax: percentage of maximal heart rate reserve; exercise HR: exercise heart rate; HRrest: resting heart rate; HRR: heart rate reserve; HRmax: maximal heart rate.

**Stage 2:** the weekly PA training on this stage will consist of one 30-min aerobic session at an intensity of 30-40% HRRmax and one prolonged aerobic session at an intensity of 35-45% HRRmax for 50 minutes.

**Stage 3:** this stage will consist of one aerobic session (30-40% HRRmax, for 45 minutes) and one higher-intensity intermittent training (shortness of breath threshold of each participant, for 1 hour) in each week.

The working load will be individualized and determined based on each participant's PA level measured at the first beginning of each stage. On each stage, each participant will be given about four weeks to adapt the training programme, when the working load and duration will be gradually increased to reach the target intensity and duration (e.g.: 30-40% HRRmax for 30 minutes on Stage 1). The strength-building component in each session, consisting of upper and lower limbs resistance training, will play an important role in improving basal metabolic rate (to speed up fat burning) and preventing physical activity related injury (PARI). The types of exercises in the intervention will be designed by both the research team and PE teachers in the study schools to eliminate the participants' boredom, avoid their attention deficit, and then to enhance their adherence to the intervention. A research assistant (RA) and the PE teachers in the study schools will deliver the intervention to the participants. The participants will also be provided with positive reinforcement and clear feedback to improve comprehension and increase confidence during exercises.

## 2. Description of control:

The participants in the control group will receive routine PE classes as usual during the intervention period (in the academic year of 2018/19).

## 3. Intervention delivery to controls after the proposed project:

Taking account of ethical issues, the participants in the control group will receive the whole intervention product right after the completion of the intervention (in the academic year of 2019/20). We will seek an internal grant's support from our university (FRG, HKBU) for it.

### (iii) Contingency / alternative plan if any problem encountered during implementation

During the intervention, any participant, no matter in which group (intervention or control), will be asked to suspend or even cease participation if being proved not to be suitable for the study any more due to any reason. For instance, if a participant is caught by a bad cold, his/her situation will be evaluated by both researchers and teachers on spot. Sh/e will be asked to keep the original plan, undertake some low-intensity activities, or skip the planned PA session, according to evaluation results. In addition, the case will be recorded and considered in data analysis and result interpretation later on. For a participant with an attendance rate below than 80%, his/her data will be excluded from data analysis. An attrition rate of 20% was therefore involved in sample size estimation to ensure a sufficient power for data analysis. In addition, intention-to-treat analysis will also be performed to avoid bias from the withdrawals.

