### (vii) Results analysis

IBM SPSS Statistics 23 will be used for data analysis. Continuous variables (e.g., BMI) will be presented with mean (standard deviation, SD) and/or median (interquartile rage, IQR) values. All continuous variables pre-intervention will be tested for between-group differences using independent sample t-test. Normality will be checked by QQ-plots, and tested for equal variance assessed by Levene's test. If skewed, the data will be logarithmically transformed before applying t-test.

A general linear model two-way repeated measure ANCOVA will be used to compare significant differences in the changes in the continuous outcome variables between the two groups, where group and time are the two factors of interest (Elmahgoub, 2011). Variables will be selected in a stepwise manner and only those with  $p < 0.1$  kept in the final models. A significance level of 0.05 will be adopted (two-tailed test). Intention-to-treat analysis will be adopted and performed to avoid bias from withdrawals or protocol deviations.

[Word Count: 2788 ]

(e) Existing Facilities:

We have all facilities needed in this project, including stadiometers, digital balance scales, Body stat 1500 MDD, Polar T31, ActiGraph accelerometers, questionnaires of subjective measurements of PA and eating habits.

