3. Incentives for participants: in order to increase the participation rate and decrease the attrition rate, a token incentive of a HK\$100 coupon (e.g. supermarket coupon) will be given to the participants competing the whole study. Thus, a total cost of HK\$6400 was estimated. In addition, rewards (e.g. stickers) will be given to the participants who complete each intervention session (a total of 72 sessions). A total of HK\$2000 was then estimated. Governance system: We will purchase coupons and stickers via the Finance Office (FO) of our university. We will ask a parent/guardian of each participant sign on the record sheet for receiving a coupon of HK\$100. The FO will monitor the disbursement of incentives to ensure accountability and traceability.
4. Conference: we will present our findings on at least an international conference. A total cost of HK\$10000 was then estimated.
5. Publication costs: We will publish at least one article in an international

peer-reviewed journal. We want it to be open access and freely available online. Open access publishing is a charged service. For example, a quality journal levies an article-processing charge of USD2785 (around HKD 21723) for each article accepted for publication. A total cost of HK\$20000 was then estimated.

6. Transportation cost: the research staff will travel between schools and office to implement the intervention. A total cost of HKD 8640 was estimated, at a rate of HKD30/travel, 72 travels/person, and 4 persons).

(ii) Estimated revenue or recurrent income (if any) to offset the expenditure of the project  
Nil

(iii) Supplementary sponsorship (monetary or non-monetary) (if any) to cover any expenditure or resource requirement of the project  
Nil

(g) Purpose and Potential:

(i) How will this project enhance your community's capacity to promote health in the long run  

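### The plan both excludes children with under 80% attendance and adopts intention-to-treat, without saying which analysis carries the conclusion or how attendance is counted

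*Combined protocol and SAP*

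**What the plan says.** Two sections deal with who is analysed.

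- **Section 13(d)(iii), Contingency / alternative plan.** The exclusion is stated without qualification: "For a participant with an attendance rate below than 80%, his/her data will be excluded from data analysis". The next sentence ties the sample size to it: "An attrition rate of 20% was therefore involved in sample size estimation to ensure a sufficient power for data analysis". ITT follows as an extra: "In addition, intention-to-treat analysis will also be performed to avoid bias from the withdrawals".
- **Section 13(d)(vii), Results analysis.** "Intention-to-treat analysis will be adopted and performed to avoid bias from withdrawals or protocol deviations". The attendance rule is not mentioned. The model is a repeated-measures general linear model (ANCOVA) with group and time as factors. No handling of missing visits is given.

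On attendance itself, the only session count is in the budget, section 13(f)(i) item 3, where rewards "will be given to the participants who complete each intervention session (a total of 72 sessions"). For the other arm, the description of control says: "The participants in the control group will receive routine PE classes as usual during the intervention period". Section 13(d)(iii) also allows an unwell child, after evaluation by researchers and teachers, to do lighter activity "or skip the planned PA session, according to evaluation results". It adds: "In addition, the case will be recorded and considered in data analysis and result interpretation later on". It does not say whether such a session counts as missed.

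**The concern.** Attendance is known only after randomisation. Children who attend well may differ from those who do not in health, motivation or family support, and these may also affect BMI change. Removing poor attenders then compares groups that randomisation did not create. ITT avoids this, which is the reason the plan itself gives for using it.

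The rule is worded for any participant, but only the intervention arm has programme sessions. The filter would therefore probably fall mainly on that arm, although the plan does not say so. If routine PE attendance were used for controls, the two arms would be screened on different behaviours. A child could also be excluded because the study's own evaluation told him or her to skip sessions.

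At stake is which result the trial reports as its finding. If the two analyses disagree, the plan does not settle it, and the choice could be made after both results are seen.

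**Working it through.** **1. The two sections side by side**

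| | 13(d)(iii) | 13(d)(vii) |
|---|---|---|
| Attendance below 80% | Data excluded | Not mentioned |
| Status of ITT | Performed as well | Adopted |
| Reason given for ITT | Withdrawals | Withdrawals or protocol deviations |
| Link to sample size | 20% allowance follows from the exclusion | None |
| Labelled primary or secondary | No | No |

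**2. The plan's own figure**

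Inputs from section 13(d)(i): 32 per group, effect size 0.722, attrition 20%. From 13(d)(vii): two-sided 0.05. The 0.722 is treated here as SD units, following its definition; the kg/m² printed beside it does not fit that definition. Power is not stated. At an assumed 80%, a two-sample t calculation gives 31.1, so 32 per group before attrition, and 32/0.8 = 40 after it. The stated 32 is therefore reproduced only without the allowance. That is a separate matter, and the present point does not depend on it.

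**3. Bias from filtering one arm**

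The documents give no attendance distribution and no correlation, so the inputs here are assumed. Let q be the share of the intervention arm excluded and r the correlation of attendance with favourable BMI change. With no true effect and a normal model:

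bias in SD units = r × φ(z_q) / (1 − q)

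For q = 0.20, z_q = −0.842 and φ = 0.280, so the multiplier is 0.280/0.80 = 0.350. For r = 0.2 the bias is 0.070, and for r = 0.3 it is 0.105. Divided by 0.722, these are 10% and 15%. Type I error is from the noncentral t with 32(1 − q) against 32:

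| Excluded | Bias, r = 0.2 | Bias, r = 0.3 | Two-sided type I error |
|---|---|---|---|
| 10% | 0.039 | 0.058 | 5.3% to 5.6% |
| 20% | 0.070 | 0.105 | 5.8% to 6.8% |
| 30% | 0.099 | 0.149 | 6.4% to 8.3% |

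At r = 0 there is no bias. At negative r the direction reverses. With a skewed (Beta) attendance distribution, also 20% excluded, the bias is 0.075 to 0.121 SD and type I error 5.9% to 7.3%. Simulation of the 20% case (100,000 trials each) gave biases of 0.070 and 0.104 and type I errors of 5.6% and 6.6%.

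**4. Both arms filtered at 20%**

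Bias = (r₁ − r₂) × 0.350, with 25.6 per arm. Equal correlations give no bias and 5.0%. With 0.2 or 0.3 in one arm and 0 in the other, the bias is 0.070 or 0.105 SD and type I error 5.7% or 6.6%. The direction depends on which arm carries the correlation.

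**5. Power (two-sided t, α = 0.05)**

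| Analysis | Effect | Numbers | Power |
|---|---|---|---|
| ITT, no dilution | 0.722 | 32 v 32 | 81% |
| ITT, 10% of intervention arm gain nothing | 0.9 × 0.722 = 0.650 | 32 v 32 | 73% |
| ITT, 20% gain nothing | 0.8 × 0.722 = 0.578 | 32 v 32 | 62% |
| Filtered, intervention arm only, 10% | 0.722 | 29 v 32 | 79% |
| Filtered, intervention arm only, 20% | 0.722 | 26 v 32 | 77% |
| Filtered, both arms, 20% | 0.722 | 26 v 26 | 72% |

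The dilution shares are assumed, and the ITT rows suppose that all 64 children are measured.

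**6. Missing visits (a related but separate point)**

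Section 13(d)(vi) schedules T1 to T4 for all participants. A repeated-measures general linear model ordinarily drops a child with any missing visit. If 5% or 10% are missing independently at each of T2, T3 and T4 (assumed), 0.95³ = 0.857 or 0.90³ = 0.729 remain, about 55 or 47 of 64. An analysis called ITT could thus become a complete-case analysis.

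**The case against.** The strongest reply is that both analyses are prespecified and the ordinary reading is clear. Section 13(d)(vii) is the analysis section and the only one to state the model and significance level. It adopts ITT against protocol deviations, of which poor attendance is a natural example. The exclusion sits under contingencies and could be read as a per-protocol set. On that view only a label is missing. This has force, but the reading must be inferred. Section 13(d)(iii) states the exclusion first, bases the attrition allowance on it and adds ITT afterwards, so a reader of that section would infer the opposite.

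Four further points bear on weight:

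- **The bias is assumed and modest.** This stands. The one-arm filter is not stated in the plan, and an equal filter in both arms gives no bias. The simulated error rates are also slightly below the analytic ones.
- **ITT can lose more power than the filter.** This stands under the dilution assumed: 62% against 72% to 77% at 20%, and 73% against 79% at 10%. It is a cost of the fix. It does not justify a post-randomisation exclusion as the main analysis.
- **72 sessions is the natural denominator.** This is fair for the intervention arm, although the figure appears only to cost rewards. Controls and skipped sessions remain undefined.
- **Missing data is a different issue.** This is correct. Withdrawal also tends to remove all later visits, so the independent-missingness figures are only illustrative.

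**Conclusion.** The concern holds. The plan gives an unqualified post-randomisation exclusion in one section and ITT in another, and nothing says which decides the conclusion. Attendance is not defined well enough to apply the rule, above all for controls. That much rests on the text alone, and confidence in it is high.

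The size of the consequence is less certain. On the assumed inputs, type I error lies between 5.3% and 8.3% if 10% to 30% of the intervention arm is excluded, with 5.8% to 6.8% in the 20% case. The direction follows the correlation between attendance and BMI change. The bias vanishes if that correlation is zero or the filter acts equally in both arms. This should be fixed before analysis, mainly to remove the choice between two main results.

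**What to change.** Reconcile sections 13(d)(iii) and 13(d)(vii) with one statement, for example: *The primary analysis includes all randomised children in the arm assigned, whatever their attendance. The set with at least 80% attendance is a secondary per-protocol analysis and does not drive the conclusion.* Then:

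- Keep measuring children who stop sessions at the scheduled T2 to T4 visits, where they and their parents or guardians are willing.
- State the missing-data handling. Use all available T1 to T4 data, for example in a likelihood-based mixed model (valid if data are missing at random) or with multiple imputation. Add a sensitivity analysis, because health may drive both absence and missing data.
- For the secondary set, define the attendance denominator in each arm, or state that the rule does not apply to controls. Say whether sessions skipped on the study's own evaluation count as missed.

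The cost is protocol and SAP wording, a little more analysis and the effort of following children who stop. No visits are added. The statistical cost is dilution: under the assumptions above, ITT power falls from 81% to 73% or 62% if 10% or 20% of the intervention arm gains nothing. The sponsor should accept this knowingly when confirming the sample size.

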1. To reduce BMI among a sample of overweight and obese adolescent children with ID in local special schools;
2. To reduce % body fat among the sample;
3. To reduce waist-to-height ratio among the sample;
4. To reduce overweight and obese status among the sample;
5. To improve PA levels among the sample.

(d) Project Plan:

[figure not shown]
(i) Target group

The target population of the project will be adolescents with mild and moderate ID (aged 12- 18 years) who are overweight and obese. We will adopt a randomised controlled trial (RCT) design and recruit 64 overweight and obese students from 4-6 special schools, and then randomly and equally assign them into the intervention and control groups (32 in each group). This sample size can test an effect size of  $0.722 \text{ kg/m}^2$  (mean difference in change of BMI divided by pooled standard deviation), with an attrition rate of 20%. The selection criteria of participants include: (1) children with mild and moderate ID; (2) aged 13-18 years old; (3) being overweight or obese; (4) without physical disability; (5) without medical predispositions towards obesity (genetic syndrome or drug treatment) that could interfere with the results of the study; and (6) without contraindications for regular physical activity (e.g. asthma, heart disease). A written informed consent will be obtained from their parents/guardians in advance.

(ii) Implementation plan

*1. Description of intervention:*

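### The 80% attendance rule does not support the 20% attrition allowance, 64 children give about 72% power (not 80%) after a 20% loss, and the plan does not say whether the attendance-restricted or the intention-to-treat analysis is primary

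*Combined protocol and SAP*

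**What the plan says.** Section 13(d)(i), Target group, plans to "recruit 64 overweight and obese students from 4-6 special schools, and then randomly and equally assign them into the intervention and control groups", which makes 32 per arm. It continues "This sample size can test an effect size of" 0.722, defined as the difference in mean BMI change over the pooled standard deviation, "with an attrition rate of 20" per cent. It gives no power and no source for the attrition figure.

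Section 13(d)(iii), Contingency plan, sets the attendance rule: "For a participant with an attendance rate below than 80%, his/her data will be excluded from data analysis". The next sentence links that rule to the sample size: "An attrition rate of 20% was therefore involved in sample size estimation to ensure a sufficient power for data analysis". The paragraph closes by adding an intention-to-treat analysis alongside.

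Section 13(d)(vii), Results analysis, states: "A significance level of 0.05 will be adopted (two-tailed test"). It adopts intention-to-treat and does not mention the attendance exclusion.

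**The concern.** Two percentages that measure different things are joined by the word *therefore*. The 80% is a share of sessions attended by one child. The 20% is a share of children missing from the analysis. The second depends on how attendance is distributed between children and on how many withdraw, and the documents give neither. The assurance of sufficient power therefore rests on a figure with no stated basis and is measured against a target that is never given.

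The rule also selects children by what happens after randomisation. Section 13(d)(ii) gives controls only their usual PE classes, so they have no programme sessions to miss. Comparing intervention children who attended well with essentially unselected controls gives up the protection of randomisation. If that analysis were taken as the main result, the estimate could be biased as well as less precise.

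**Working it through.** **Inputs from the documents**
- 32 per arm, 20% attrition and effect size d = 0.722: section 13(d)(i). The figure is printed with kg/m² but defined as a ratio to a standard deviation, so it is used here as a standardised difference.
- Two-sided 0.05: section 13(d)(vii).
- 80% attendance rule: section 13(d)(iii). Total of 72 sessions: section 13(f).

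**Assumptions**
- Target power is not stated; 80% is taken as the conventional benchmark.
- The comparison is a two-sample test of BMI change, which matches the definition of the effect size. Nothing is added or subtracted for school, covariates or repeated measures.

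**Step 1. Reproducing 64.** Per arm, n = 2(z₀.₉₇₅ + z_power)² / d². At 80% power this is 2(1.960 + 0.842)² / 0.722² = 15.70 / 0.521 = 30.1, so 31. The t-test gives 31.1, so 32. The planned 32 per arm is thus what 80% power needs before any loss. Allowing for 20% loss gives 31/0.8 = 38.75, so 39, or 32/0.8 = 40, a total of 78 to 80.

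Because power is not stated, 64 cannot be reproduced uniquely. Two other settings do give 32 per arm after a 20% inflation, since each needs 25 per arm by t-test and 25/0.8 = 31.25, so 32:
- a two-sided test at 70% power;
- a one-sided 0.05 test at 80% power, which conflicts with the two-tailed test in section 13(d)(vii).

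**Step 2. Power of the planned number.** The normal approximation is Φ(d√(n/2) − 1.960). With n = 32: Φ(0.722 × 4 − 1.960) = Φ(0.928) = 82.3%. With n = 26: Φ(2.603 − 1.960) = Φ(0.643) = 74.0%. The t-test values are slightly lower.

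| Loss in both arms | n per arm | Normal | t-test |
|---|---|---|---|
| 0% | 32 | 82.3% | 81.1% |
| 10% | 28.8 | 78.2% | 76.8% |
| 20% | 25.6 | 73.3% | 71.6% |
| 20%, whole children | 26 | 74.0% | 72.3% |
| 30% | 22.4 | 67.6% | 65.6% |

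If 20% of the intervention arm alone is lost (25.6 v 32), t-test power is 76.3%.

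**Step 3. Does the cut-off fix the share of children lost?** 0.80 × 72 = 57.6, so a child with 57 or fewer sessions is excluded. The share excluded is P(X ≤ 57) for X out of 72, taken as binomial (intraclass correlation 0) or beta-binomial. Mean attendance and the correlation are assumptions.

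| Mean attendance | ICC 0 | ICC 0.1 | ICC 0.2 |
|---|---|---|---|
| 80% | 47.6% | 42.9% | 39.7% |
| 85% | 11.4% | 27.9% | 28.4% |
| 90% | 0.5% | 14.7% | 17.5% |

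The same rule is compatible with anything from 0.5% to 48% excluded.

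**Step 4. Which analysis is primary?** Section 13(d)(iii) states the exclusion as the rule and intention-to-treat as an addition. Section 13(d)(vii) adopts intention-to-treat and is silent on the exclusion. An analysis that drops low attenders is not intention-to-treat, so these are two different analyses, and the plan ranks neither.

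**The case against.** Several stronger readings are tempting, and the documents do not support them.

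- **The 20% was obtained as 100% minus 80%.** No such calculation is written. Section 13(d)(i) gives the 20% without reference to attendance, and *therefore* may mean only that some allowance was needed because some children would be dropped. On that reading the 20% simply has no stated basis.
- **The allowance ignores ordinary withdrawal.** The same paragraph of section 13(d)(iii) opens with children in either group ceasing participation, and the figure is called attrition. It may be meant to cover both sources of loss.
- **All exclusions fall on the intervention arm.** This is likely but not stated. The rule refers to participants generally, and attendance is left undefined for controls.
- **The restricted analysis would fall far below the planned number.** If 40% of the intervention arm alone were excluded, 19 v 32 = 51 children would remain, against 26 v 26 = 52 under the 20% allowance. Power would be 68.6% rather than 72.3%. Even this case rests on an assumed mean attendance of 80%.

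It is also fair that intention-to-treat is already planned, and that section 13(d)(vi) has the obesity indicators measured at T1 to T4 in all participants. Low attenders stay in the intention-to-treat analysis, whose power is about 81% if all 64 are measured. That limits the harm of the exclusion rule. It does not settle which result is the main one, and it does not restore 80% power once 20% of outcomes are missing.

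**Conclusion.** The point holds in a limited form. The attendance cut-off does not justify a 20% loss, nothing else in the documents does, and no target power is given. If 20% are lost, power at 0.722 is about 72%, against 81% with no loss, a difference of about 9 points. This shortfall comes mainly from 64 being the number needed with no loss at 80% power, and it does not depend on any assumption about attendance. It does depend on reading 0.722 as a standardised difference, on the two-sided 0.05 test and on a simple two-group comparison. Calling it a shortfall also takes 80% as the benchmark.

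The second part is qualitative. A post-randomisation exclusion that controls are unlikely to trigger can bias the analysis that uses it, and the plan leaves open whether that analysis is primary. The size of any such bias, and the number of children below 80% attendance, cannot be known from the documents.

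**What to change.** In section 13(d)(iii):
- delete *therefore* and separate the attendance rule from the sample size statement;
- name intention-to-treat, with no attendance exclusion, as the primary analysis;
- label the attendance-restricted analysis secondary and say how attendance is defined for controls, if at all.

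In section 13(d)(i):
- define the 20% as the expected share of randomised children without T4 BMI, with its basis;
- state the target power, and report that 32 per arm gives about 72% at 20% loss and 81% with none.

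In section 13(d)(vii), repeat the same primary and secondary labels.

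The cost is wording and a stated power about 9 points lower than with full follow-up; no extra participants are needed. If the sponsor prefers to hold 80% power after a 20% loss, the price is 78 to 80 children instead of 64.
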